15.2 Secondary objectives

1. **Assessment of the safety profile of the VORTX Rx®.**

This objective is given the answer with the analyses proposed in sections 6.7.2, 6.7.3, 6.7.4, 6.7.5, 6.8, 8.2, 8.3, 8.4, 9.2, 9.3, 9.4, 9.5, 10.2, 10.3, 10.4, 10.5, 11.2, 11.3, 11.4, 11.5 and 12 of this document.

2. **Assessment of local tumor progression by MRI at 1 week, 1 month and 2 months, post-procedure.**

The following analyses will be carried out to respond to this objective:

The number of patients who have indicated local tumor progression **in at least one visit** (1 week, 1 month, 2 months) for each tumor ablated in ablation 1, ablation 2, and ablation 3 will be provided.

3. **Assessment of the involution of the ablation zone 1 week, 1 month and 2 months post-procedure.**

The following analyses will be carried out separately for each tumor (tumor 1, tumor 2, tumor 3....) to respond to this objective:

- Ablation zone volume at 24 hours post-ablation, 1-week, 1 month and 2 months post-ablation will be compared among visit using a general linear model of repeated measures.

In addition:

- Ablation zone volume at 24 hours post ablation vs ablation zone volume at 1 week will be compared using Paired T-Test or Wilcoxon depending on variable distribution.
- Ablation zone volume at 24 hours post ablation vs ablation zone volume at 1 month will be compared using Paired T-Test or Wilcoxon depending on variable distribution.
- Ablation zone volume at 24 hours post ablation vs ablation zone volume at 2 months will be compared using Paired T-Test or Wilcoxon depending on variable distribution.

4. **Assessment of liver panel.**

The following analyses will be carried out separately for each ablation (ablation 1, ablation 2, ablation 3) to respond to this objective:

- AST at Screening and at 24 hours post-procedure and the follow-up visits performed at 1 week, and 1 and 2 months post-procedure will be compared among visit using a general linear model of repeated measures.
- ALT at Screening and at 24 hours post-procedure and the follow-up visits performed at 1 week, and 1 and 2 months post-procedure will be compared among visit using a general linear model of repeated measures.
- GGT at Screening and at 24 hours post-procedure and the follow-up visits performed at 1 week, and 1 and 2 months post-procedure will be compared among visit using a general linear model of repeated measures.

- Alkaline phosphatase at Screening and at 24 hours post-procedure and the follow-up visits performed at 1 week, and 1 and 2 months post-procedure will be compared among visit using a general linear model of repeated measures.
- Total bilirubin at Screening and at 24 hours post-procedure and the follow-up visits performed at 1 week, and 1 and 2 months post-procedure will be compared among visit using a general linear model of repeated measures.
- Albumin at Screening and at 24 hours post-procedure and the follow-up visits performed at 1 week, and 1 and 2 months post-procedure will be compared among visit using a general linear model of repeated measures.
- Prothrombine (PT) at Screening and at 24 hours post-procedure and the follow-up visits performed at 1 week, and 1 and 2 months post-procedure will be compared among visit using a general linear model of repeated measures.
- INR at Screening and at 24 hours post-procedure and the follow-up visits performed at 1 week, and 1 and 2 months post-procedure will be compared among visit using a general linear model of repeated measures.

5. Immunologic assessment.

The following analyses will be carried out separately for each ablation (ablation 1, ablation 2, ablation 3) to respond to this objective:

- CD3+ at Screening and at 24 hours post-procedure and the follow-up visits performed at 1 week, and 1 and 2 months post-procedure will be compared among visit using a general linear model of repeated measures.
- CD4+ at Screening and at 24 hours post-procedure and the follow-up visits performed at 1 week, and 1 and 2 months post-procedure will be compared among visit using a general linear model of repeated measures.
- CD8+ at Screening and at 24 hours post-procedure and the follow-up visits performed at 1 week, and 1 and 2 months post-procedure will be compared among visit using a general linear model of repeated measures.
- CD45+ at Screening and at 24 hours post-procedure and the follow-up visits performed at 1 week, and 1 and 2 months post-procedure will be compared among visit using a general linear model of repeated measures.
- CD16+ at Screening and at 24 hours post-procedure and the follow-up visits performed at 1 week, and 1 and 2 months post-procedure will be compared among visit using a general linear model of repeated measures.

- CD56+ at Screening and at 24 hours post-procedure and the follow-up visits performed at 1 week, and 1 and 2 months post-procedure will be compared among visit using a general linear model of repeated measures.
- CD19+ at Screening and at 24 hours post-procedure and the follow-up visits performed at 1 week, and 1 and 2 months post-procedure will be compared among visit using a general linear model of repeated measures.
- C reactive protein at Screening and at 24 hours post-procedure and the follow-up visits performed at 1 week, and 1 and 2 months post-procedure will be compared among visit using a general linear model of repeated measures.
- Complement C3 at Screening and at 24 hours post-procedure and the follow-up visits performed at 1 week, and 1 and 2 months post-procedure will be compared among visit using a general linear model of repeated measures.
- Complement C4 at Screening and at 24 hours post-procedure and the follow-up visits performed at 1 week, and 1 and 2 months post-procedure will be compared among visit using a general linear model of repeated measures.
- Complement CH50 at Screening and at 24 hours post-procedure and the follow-up visits performed at 1 week, and 1 and 2 months post-procedure will be compared among visit using a general linear model of repeated measures.
- IgG at Screening and at 24 hours post-procedure and the follow-up visits performed at 1 week, and 1 and 2 months post-procedure will be compared among visit using a general linear model of repeated measures.
- IgM at Screening and at 24 hours post-procedure and the follow-up visits performed at 1 week, and 1 and 2 months post-procedure will be compared among visit using a general linear model of repeated measures.
- IgA at Screening and at 24 hours post-procedure and the follow-up visits performed at 1 week, and 1 and 2 months post-procedure will be compared among visit using a general linear model of repeated measures.
- Interleudin-6 at Screening and at 24 hours post-procedure and the follow-up visits performed at 1 week, and 1 and 2 months post-procedure will be compared among visit using a general linear model of repeated measures.
- CEA at Screening and at 24 hours post-procedure and the follow-up visits performed at 1 week, and 1 and 2 months post-procedure will be compared among visit using a general linear model of repeated measures.
- AFP at Screening and at 24 hours post-procedure and the follow-up visits performed at 1 week, and 1 and 2 months post-procedure will be compared among visit using a general linear model of repeated measures.

- CA 15-3 at Screening and at 24 hours post-procedure and the follow-up visits performed at 1 week, and 1 and 2 months post-procedure will be compared among visit using a general linear model of repeated measures.
- CA 19-9 at Screening and at 24 hours post-procedure and the follow-up visits performed at 1 week, and 1 and 2 months post-procedure will be compared among visit using a general linear model of repeated measures.

6. Evaluation of quality of life.

The following analyses will be carried out separately for each ablation (ablation 1, ablation 2, ablation 3) to respond to this objective:

- Global health status/QoL (revised) at Screening and 1 and 2 months post-procedure will be compared among visit using a general linear model of repeated measures.
- Physical functioning (revised) at Screening and 1 and 2 months post-procedure will be compared among visit using a general linear model of repeated measures.
- Role functioning (revised) at Screening and 1 and 2 months post-procedure will be compared among visit using a general linear model of repeated measures.
- Emotional functioning at Screening and 1 and 2 months post-procedure will be compared among visit using a general linear model of repeated measures.
- Cognitive functioning at Screening and 1 and 2 months post-procedure will be compared among visit using a general linear model of repeated measures.
- Social functioning at Screening and 1 and 2 months post-procedure will be compared among visit using a general linear model of repeated measures.
- Fatigue at Screening and 1 and 2 months post-procedure will be compared among visit using a general linear model of repeated measures.
- Nausea and vomiting at Screening and 1 and 2 months post-procedure will be compared among visit using a general linear model of repeated measures.
- Pain at Screening and 1 and 2 months post-procedure will be compared among visit using a general linear model of repeated measures.
- Dyspnoea at Screening and 1 and 2 months post-procedure will be compared among visit using a general linear model of repeated measures.
- Insomnia at Screening and 1 and 2 months post-procedure will be compared among visit using a general linear model of repeated measures.
- Appetite loss at Screening and 1 and 2 months post-procedure will be compared among visit using a general linear model of repeated measures.

- Constipation at Screening and 1 and 2 months post-procedure will be compared among visit using a general linear model of repeated measures.
- Diarrhoea at Screening and 1 and 2 months post-procedure will be compared among visit using a general linear model of repeated measures.
- Financial difficulties at Screening and 1 and 2 months post-procedure will be compared among visit using a general linear model of repeated measures.

7. **Assessment of pain and analgesic requirements after the ablation procedure.**

The following analyses will be carried out separately for each ablation (ablation 1, ablation 2, ablation 3) to respond to this objective:

- VAS score at screening, at 24 hours post-procedure and the follow-up visits performed at 1 week, will be compared among visit using a general linear model of repeated measures.

In addition, the following categorical variable will be described (n, %) (this analysis will be carried out for the total patients):

- Number of patients with at least one drug due to Post-procedure pain (concomitant medication form).

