3.2 Study population

This study will include up to ten (10) subjects meeting all the inclusion criteria and none of the exclusion criteria, and giving their informed consent to participate in the study.

Inclusion criteria

1. Written informed consent before any study procedure is performed.
2. Subjects of both sexes aged 18 years or older.
3. Patients diagnosed with liver cancer, including HCC or liver metastases from breast, lung, pancreas and/or colorectal cancers. If biopsy is required, there will be a minimum of 2-week period after biopsy and before the ablation.
 - HCC patients must meet the United Network for Organ Sharing and Organ Procurement and Transplantation Network (UNOS-OPTN) class 5 criteria for HCC
 - Liver metastases patients must meet minimum criteria of liver biopsy and/or tissue diagnosis of primary tumor or metastatic tumor with new or growing liver tumors radiologically consistent with metastases.
4. Patients with liver cancer not candidates for surgical resection and/or not suitable for other locoregional treatments or patients who have not responded to or relapsed from conventional therapies.
5. Previous treatment with chemotherapy and/or radiotherapy is permitted provided that these treatments have been discontinued more than 2 weeks before the ablation of the targeted tumor and whenever patients have recovered from any related toxicity.
6. Previous treatment with immunotherapies is permitted provided that these therapies have been discontinued at least 4 weeks before the ablation and whenever patients have recovered from any related toxicity.
7. Previous ablation/surgery on other tumors different from those that will be targeted with the VORTX Rx® is allowed whenever a minimum of 2 weeks has elapsed since the prior procedure(s).
8. Tumor(s) to be targeted for ablation will be clearly separated from other tumors or other critical areas upon investigator's criteria.
9. Largest diameter of targeted tumor(s) ≤ 3 cm.
10. Tumor(s) that will be targeted at a depth < 10 cm from the skin surface.
11. Must have an adequate acoustic window in the abdominal space to be able to visualize targeted tumor(s) using ultrasound imaging; also, must be able to visualize targeted tumor using MRI with optional CT imaging at investigator discretion.
12. Patients who can safely undergo general anaesthesia.

13. Liver function score of Child-Pugh A or Child-Pugh B.
14. ECOG PS 0, 1 or 2 at screening.

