15. Adequate liver function (ALT and AST < 2.5 x upper limit of normal [ULN]), renal function (serum creatinine <2 ULN and/or bilirubin <2.5 UNL) and hematologic function (neutrophil count > 1.0 x 10⁹/L and platelet > 50 x 10⁹/L).
16. An INR <2 within the last 7 days prior to the ablation in patients receiving anticoagulants, and an INR <1.5 for patients not treated with anticoagulants.
17. Platelets level >50 x 10⁹/L within the last 7 days prior to the ablation

Exclusion criteria

1. Patients who decline or are unable to understand, provide or are unwilling to sign an informed consent form.
2. Pregnant or nursing (lactating) women; women of childbearing potential and sexually active that are unwilling to use adequate contraception (such as oral contraceptives, intrauterine contraceptive device or barrier method with spermicide or surgical sterilization).
3. Targeted tumor(s) not clearly separated.
4. Targeted tumor(s) >3 cm.
5. Tumor that will be targeted >10 cm from the skin surface.
6. Tumor not clearly visible with diagnostic ultrasound and MRI.
7. Liver function score of Child-Pugh C.
8. Liver volume reserve <40% as measured by CT Scan.
9. Major surgical procedure, biopsy or significant traumatic injury <2 weeks prior to the procedure or has not recovered from side effects/complications of such procedure or trauma.
10. Patient who has not recovered to grade 1 or better from any AEs (except alopecia, fatigue, nausea, vomiting) related to previous anti neoplastic therapies.
11. BMI >30.
12. Parkinson's disease.
13. History of bleeding disorders (e.g. von Willebrand disease) or patients suspected to have a bleeding disorder.
14. Not able to temporarily discontinue warfarin, clopidogrel or any other long-acting anticoagulants at least two weeks before the procedure.
15. Initiation of any anticancer treatment during the screening period.
16. Life expectancy to be less than 6 months.
17. ASA score ≥ 4.

18. Unable or unwilling to complete all required screening and/or follow-up assessments.
19. Patients under ongoing treatment with an investigational medication or medical device that conflicts with the study device.
20. Patients for whom the investigator considers that the ablation is not in the patient's best interest.
21. Patients with active alcohol or drug addiction or any other condition that, in the investigator's opinion, would interfere with their ability to comply with the study requirements.

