4 METHODOLOGY

Quantitative variables will be described with measures of central tendency and dispersion: mean, median, SD (standard deviation), Q1 (first quartile) and Q3 (third quartile), minimum and maximum).

Qualitative variables will be described using absolute and relative frequencies (N, %). Two percentage columns will be presented, total percentage (total %) and valid percentage (valid %), that is, the percentage over the sum of valid responses plus missing values and the percentage over the total of valid responses. When there will be not missing values both of them will be equal, and then only one will be shown.

In the analysis of parameters evolution (ablation zone, liver function parameters, immunological parameters, quality of life scores, VAS scale score), among visits, general linear models of repeated measures will be used. With this methodology, it is necessary that the values of the variable must be available at all visits for all patients.

Where an inferential analysis is required, parametric tests shall be used for continuous variables (T-test) that follow a normal distribution. For variables that do not follow a normal (or non parametric) distribution, Mann Whitney (for unpaired data) or Wilcoxon (for paired data) hypothesis tests shall be used.

These tests will be used in all bilateral cases and with a level of significance of 0.05. In cases where a p-value less than 0.05 appears, it refers to the existence of statistical significance.

Due to the number of evaluable patient ablations available, any result from an applied statistical test must be interpreted with caution.

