8.4 Laboratory test

The following analyses will be carried out separately for each ablation procedure (ablation 1, ablation 2 and ablation 3):

Descriptive statistics (mean, SD, median, Q_1 , Q_3 , minimum, maximum) of the following continuous variables will be shown:

- Haemoglobin
- Erythrocytes
- Leucocytes
- Neutrophils
- Basophils
- Haematocrit
- Lymphocytes
- Monocytes
- Eosinophils
- Platelets
- AST
- ALT
- GGT
- Alkaline phosphatase
- Total bilirubin
- Albumin
- Prothrombine (PT)
- INR
- Partial thromboplastin time
- Glucose
- Calcium
- Sodium
- Potassium
- Bicarbonate
- Chloride
- BUN
- Creatinine
- CD3+
- CD4+
- CD8+
- CD45+
- CD16+
- CD56+
- CD19+
- C reactive protein

- Complement C3
- Complement C4
- Complement CH50
- IgG
- IgM
- IgA
- Interleukin-6
- CEA
- AFP
- Ca 15-3
- Ca 19-9

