8.5 Child-Pugh score

The following analyses will be carried out separately for each ablation procedure (ablation 1, ablation 2 and ablation 3):

Child-Pugh score and Child-Pugh category will be calculated according to the following rules:

Child-Pugh Score and Interpretation			
Classification	1	2	3
Serum bilirubin (µmol/L)	<34	34-51	>51
Serum albumin (g/L)	>35	28-35	<28
Presence of ascites	Absent	Controllable	Refractory
Encephalopathy	Absent	Minimal	Severe
INR	<1.7	1.7-2.3	>2.3
Interpretation			
Points	Class	Life Expectancy	Perioperative Mortality
5-6	A	15-50 yrs	10%
7-9	B	Candidate for transplant	30%
10-15	C	1-3 months	82%

The categorical variable to be described (n, %) is:

- Child-Pugh category

Descriptive statistics (mean, SD, median, Q₁, Q₃, minimum, maximum) of the following continuous variable will be shown:

- Child-Pugh score

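### The laboratory, vital-sign and ECOG tables named for the safety objective are separate per-visit summaries and cannot reliably separate new deterioration from an abnormal entry value

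*SAP*

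**What the plan says.** Section 15.2 item 1 adds no analysis of its own. It states "This objective is given the answer with the analyses proposed in sections 6.7.2, 6.7.3, 6.7.4, 6.7.5, 6.8, 8.2, 8.3, 8.4", then names 9.2 to 9.5, 10.2 to 10.5, 11.2 to 11.5 and section 12.

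The cited visit sections all have the same form. Laboratory values and vital signs get mean, SD, median, quartiles, minimum and maximum "of the following continuous variables will be shown" (for example section 8.4). Physical examination and ECOG get counts and percentages at that visit. None of them defines a change from screening, a shift, an abnormality flag or a patient listing.

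Section 4 reserves comparison between visits for a named list: "In the analysis of parameters evolution (ablation zone, liver function parameters, immunological parameters, quality of life scores, VAS scale score), among visits". Items 3 to 7 of 15.2 follow that list. Two coagulation measures fall inside it, under the liver panel in item 4: "Prothrombine (PT) at Screening and at 24 hours post-procedure and the follow-up visits performed at 1 week" and "INR at Screening and at 24 hours post-procedure and the follow-up visits performed at 1 week", each with a repeated-measures model.

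Child-Pugh is calculated at every visit except the procedure itself (6.9, 8.5, 9.6, 10.6, 11.6), and the category is summarised as "The categorical variable to be described (n, %) is". Item 1 does not cite those sections, and item 4 does not include the score or class.

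Entry is open to patients with abnormal values: "Liver function score of Child-Pugh A or Child-Pugh B", "serum creatinine <2 ULN and/or bilirubin <2.5 UNL", ECOG 0 to 2, platelets above 50 x 10⁹/L and neutrophils above 1.0 x 10⁹/L (section 3.2).

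**The concern.** With up to ten patients, the useful safety question for a laboratory test or performance status is whether any individual got worse after the procedure. A summary of all values at one visit, set beside a summary of all values at another, discards the link between a patient's two values. When some patients enter abnormal, a high maximum or low minimum after the procedure may be an entry value carried forward, or it may be new. The tables named as safety evidence do not say which.

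The gap is selective. Every QLQ-C30 scale, including financial difficulties, is compared across visits, while platelets, haemoglobin, neutrophils, creatinine and ECOG are not.

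The layout adds a second difficulty. Screening is summarised once for all patients, but follow-up is split by ablation 1, 2 and 3. For the later ablations the follow-up table need not cover the same patients as the screening table.

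**Working it through.** The SAP gives no figure for this point, so there is none to reproduce. The check is what the planned tables can and cannot distinguish. N = 10 is the stated maximum (section 3.2); all patient values below are assumptions chosen within the entry criteria.

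**1. Which parameters lack a within-patient comparison.** Setting the section 4 list and 15.2 items 3 to 7 against the laboratory list in 6.8 leaves haematology, BUN and creatinine, electrolytes and partial thromboplastin time without one. Vital signs and ECOG are also outside the list. AST, ALT, GGT, alkaline phosphatase, bilirubin, albumin, PT and INR are covered by item 4.

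**2. ECOG.** Assume counts for ECOG 0/1/2 of 4/4/2 at screening and again at follow-up. Enumerating every 3 x 3 transition table with those margins gives 0, 1, 2, 3, 4, 5 or 6 worsened patients. Six is reached by four patients moving 0 to 1, two moving 1 to 2, two moving 1 to 0 and two moving 2 to 0. The margins stay 4/4/2, and the planned tables are the same in every case.

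**3. Child-Pugh.** One patient moving A to B and one moving B to A leaves both visit counts unchanged.

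**4. Creatinine, full cancellation.** Assume screening values (x ULN) of 0.6, 0.7, 0.7, 0.8, 0.9, 1.0, 1.1, 1.3, 1.6, 1.9. Mean 1.06, SD 0.42, median 0.95, Q1 0.725, Q3 1.25, minimum 0.6, maximum 1.9. Suppose the same ten values appear at follow-up:

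- unchanged in each patient: 0 newly above ULN, 0 with a rise of 1.5-fold or more;
- reversed across patients: 4 newly above ULN (0.6 to 1.9, 0.7 to 1.6, 0.7 to 1.3, 0.8 to 1.1), of which 3 rise at least 1.5-fold (3.17, 2.29 and 1.86).

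All seven planned statistics are identical. This case needs other patients to improve by mirrored amounts.

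**5. Creatinine, no patient improves.** From the same screening values, take the follow-up set 0.6, 0.7, 0.8, 0.9, 1.0, 1.1, 1.3, 1.6, 1.9, 1.9. It arises in either of two ways:

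- one patient goes from 0.7 to 1.9 and nine are stable: 1.9/0.7 = 2.7-fold;
- seven patients rise slightly (0.7 to 0.8, 0.8 to 0.9, 0.9 to 1.0, 1.0 to 1.1, 1.1 to 1.3, 1.3 to 1.6, 1.6 to 1.9) and three are stable: the largest ratio is 1.6/1.3 = 1.23.

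Both give mean 1.18 (up 1.2/10 = 0.12), SD 0.48, median 1.05, Q1 0.825, Q3 1.525, minimum 0.6 and an unchanged maximum of 1.9. The summaries do move, but they do not show whether one patient was harmed.

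**6. Platelets.** One patient stable at 55 and another falling from 180 to 60, the rest stable: the minimum stays at 55 and the mean falls by (180 - 60)/10 = 12.

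**7. In general.** With equal SD at two visits, SD of change = SD x √(2(1 - r)), where r is the within-patient correlation. For r = 0, 0.5, 0.8 and 0.95 this is 1.41, 1.00, 0.63 and 0.32 times the visit SD. Per-visit summaries carry no information on r.

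**The case against.** Several stronger readings are tempting, and the SAP does not support them.

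- *Individual harm is invisible in the safety analysis.* Item 1 also names section 12, which counts patients by event at maximum grade, separates device-related and procedure-related events, and lists serious events by patient. A deterioration recorded as an adverse event is therefore visible. Whether a laboratory worsening must be so recorded is a protocol matter and cannot be judged here. The limitation applies to the laboratory, vital-sign and ECOG tables.
- *Coagulation is not compared across visits.* PT and INR are; only partial thromboplastin time is left out.
- *Only the liver and immune panels are modelled within patient.* Ablation volume, quality of life and VAS are modelled too, and so are three Child-Pugh components (bilirubin, albumin, INR).
- *The summaries would show no change if one patient collapsed.* If one worsens and the others are stable, the mean must move. Wholly unchanged summaries need offsetting improvements.

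It can also be said that a follow-up value beyond an entry limit is necessarily new, because eligible patients start inside those limits, and the planned minimum or maximum would reveal it. That is right for such values. It does not help with large changes inside the limits: creatinine 1.9 is below 2 x ULN and platelets of 60 are above 50.

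What remains is that tables named as safety evidence do not identify an individual's change. The item 4 models do not fill this gap even for the liver panel: they test an average, and section 4 requires values at all visits for all patients.

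**Conclusion.** The point holds for the laboratory, vital-sign and ECOG outputs under 15.2 item 1. Haematology, creatinine and BUN, electrolytes, partial thromboplastin time, vital signs and ECOG have no within-patient comparison with screening, and Child-Pugh class is summarised by visit but used for no objective. Because abnormal values are allowed at entry, these tables cannot reliably separate new deterioration from an abnormal start.

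The size depends on data not yet seen. Under the assumed values, the ambiguity runs from 0 to 6 of ten patients for ECOG and from 0 to 4 of ten newly above ULN for creatinine; these are illustrations of what the tables leave open, not predictions. This is an inexpensive improvement to the analysis and worth making before the final analysis. It does not show that the safety section as a whole would miss harm.

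**What to change.** In 15.2 item 1, add:

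1. For each safety laboratory test and vital sign, the change (or ratio) from the patient's own last value before the first ablation to the worst value after it, with the direction that counts as worse stated for each variable.
2. Shift tables of baseline against worst post-ablation value for ECOG and Child-Pugh class, with the Child-Pugh sections (6.9, 8.5, 9.6, 10.6, 11.6) added to the sections cited.
3. A by-patient listing of values by visit and ablation number, which is practical for at most ten patients.
4. A statement of which baseline applies to ablations 2 and 3.

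The eligibility limits should not be the only laboratory categories. Eligible patients start inside them, so the baseline side of such a table would have a single category. Both worked examples (creatinine 0.7 to 1.9 x ULN, platelets 180 to 60) would count as no worsening, and section 3.2 gives no limit for haemoglobin or partial thromboplastin time.

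The cost is a few programmed tables and listings from data already collected, with no new measurements. The downside is a slightly longer report.

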5 ANALYSIS SETS

5.1 Full analysis set

The full analysis set includes all of targeted tumors ablated from all patients who have undergone an ablation with the investigational device.

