6.12 Baseline imaging of the target tumor

The categorical variables to be described (n, %) are:

- Technique used for tumor imaging:
 - Magnetic resonance imaging
 - Computed tomography

- Ultrasound with contrast
- Ultrasound without contrast

Descriptive statistics (mean, SD, median, Q₁, Q₃, minimum, maximum) of the following continuous variable will be shown:

- Number of targeted tumors planned to be ablated

The following analyses will be carried out for total targeted tumors (tumor 1 + tumor 2 + tumor 3....):

Descriptive statistics (mean, SD, median, Q₁, Q₃, minimum, maximum) of the following continuous variables will be shown:

- Tumor location: liver segment
- Tumor size:
 - X-axis greatest dimension
 - Y-axis greatest dimension
 - Z-axis greatest dimension
- Volume
- Expected ablation volume

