8.6 Post-procedure imaging

The following analyses will be carried out separately for each ablation (ablation 1, ablation 2 and ablation 3):

The categorical variables to be described (n, %) are:

- Technique used for tumor imaging:
 - Magnetic resonance imaging
 - Computed tomography
 - Ultrasound with contrast
 - Ultrasound without contrast
- Damage to the integrity of vital anatomical structures, if yes
 - Mayor vessels, specify
 - Organs, specify

The following analyses will be carried out separately for total targeted tumors (tumor 1 + tumor 2 + tumor 3....):

Descriptive statistics (mean, SD, median, Q₁, Q₃, minimum, maximum) of the following continuous variables will be shown:

- X-axis greatest dimension
- Y-axis greatest dimension
- Z-axis greatest dimension
- Diameter D
- Ablation zone volume

The categorical variable to be described (n, %) is:

- Technical success

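### Ablation-zone involution is tested only by tumour number; no overall within-tumour change from 24 hours with a confidence interval is planned

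*SAP*

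**What the plan says.** - **The tests.** Section 15.2, item 3, opens with "The following analyses will be carried out separately for each tumor (tumor 1, tumor 2, tumor 3....) to respond to this objective". Within each tumour number it plans one repeated-measures general linear model over 24 hours, 1 week, 1 month and 2 months. It then adds three paired comparisons against 24 hours, the first being "Ablation zone volume at 24 hours post ablation vs ablation zone volume at 1 week will be compared using Paired T-Test or Wilcoxon", with the choice depending on the distribution. No size of change and no interval is named.
- **The pooled tables.** Section 8.6 describes ablation-zone volume "separately for total targeted tumors (tumor 1 + tumor 2 + tumor 3" and so on, and sections 9.7, 10.7 and 11.7 do the same at the later visits. These are summaries of the volume at each visit: mean, SD, median, quartiles and range.
- **The analysis set.** Section 5.1 is defined on tumours: "The full analysis set includes all of targeted tumors ablated from all patients who have undergone an ablation with the investigational device".
- **Size and caveats.** Section 3.2: "This study will include up to ten (10) subjects meeting all the inclusion criteria". Section 4 says of the repeated-measures model that "it is necessary that the values of the variable must be available at all visits for all patients", and warns that "any result from an applied statistical test must be interpreted with caution".
- **The labels.** Section 6.12 uses the same numbering at baseline imaging ("The following analyses will be carried out for total targeted tumors (tumor 1 + tumor 2 + tumor 3"). That suggests numbering within each patient, but no section says so, or says how numbers carry over to a second or third procedure.

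**The concern.** The objective asks how the ablation zone involutes after the procedure. A tumour number is, as far as the SAP shows, a record label and not a question of interest. Splitting by it has three effects:

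1. The objective receives four tests per tumour number. If some patients have several tumours, no statement ranks the result for tumour 1 against that for tumour 2 or 3.
2. The strata for tumours 2 and 3 contain only patients with that many tumours. In a trial of up to ten patients they may be very small, so strata can disagree merely because of their size.
3. The reader never receives the quantity of interest: how much a zone shrinks from its own 24-hour volume, and how uncertain that is. The visit tables do not supply it. With complete data the mean absolute change is the difference between two tabulated means. Its interval cannot be derived from the tables, because it needs each tumour's own change and must allow for several tumours in one patient.

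**Working it through.** The SAP states no sample-size, power or precision figure for involution, so there is no figure to reproduce. It also gives no tumour counts, SDs or expected involution; those below are assumptions shown as ranges.

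**Step 1. What a small stratum can show.** On the Wilcoxon branch, the smallest exact two-sided p-value for n pairs is 2/2^n:

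- n = 3: 2/8 = 0.25
- n = 4: 2/16 = 0.125
- n = 5: 2/32 = 0.0625
- n = 6: 2/64 = 0.031

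With five or fewer tumours, p < 0.05 is out of reach even if every zone shrinks. The paired t-test has no such floor, but its power is low at these sizes.

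**Step 2. Precision of one estimate against tumour 1 alone.** Assume ten patients with complete data, numbering within patient, and a common SD of percent change. Let ICC be the correlation of changes between tumours of one patient. A patient with k tumours has a mean change with variance SD² × [ICC + (1 − ICC)/k]. Tumour 1 alone has variance SD² in every patient. Both analyses have n = 10, so the ratio of interval widths is about the square root of the average bracket over the ten patients.

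| Tumours in 10 patients | Patients with 1 / 2 / 3 tumours | Average bracket, ICC 0.2 | Average bracket, ICC 0.8 | Interval narrower by |
|---|---|---|---|---|
| 12 | 8 / 2 / 0 | 0.920 | 0.980 | 1–4% |
| 15 | 6 / 3 / 1 | 0.827 | 0.957 | 2–9% |
| 17 | 5 / 3 / 2 | 0.773 | 0.943 | 3–12% |
| 20 | 3 / 4 / 3 | 0.680 | 0.920 | 4–18% |

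One entry in full, 17 tumours at ICC 0.2: k = 1 gives 1, k = 2 gives 0.6, k = 3 gives 0.467. The average is (5 × 1 + 3 × 0.6 + 2 × 0.467)/10 = 0.773, whose square root is 0.879, so the interval is 12% narrower.

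**Step 3. The same in points, with SD 20 and 17 tumours.** The expected half-width is t(0.975, n − 1)/√n × SD × c, where c is the small-sample factor for the mean of the sample SD (0.973 at n = 10, 0.940 at n = 5).

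- Tumour 1, n = 10: 0.715 × 20 × 0.973 = 13.9 points.
- Tumour 2, n = 3 + 2 = 5: 1.242 × 20 × 0.940 = 23.3 points.
- Per-patient means: 13.9 × 0.879 = 12.2 (ICC 0.2) to 13.9 × 0.971 = 13.5 (ICC 0.8).

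**Step 4. Validity of the interval.** In simulation, the t-interval on per-patient means covered about 95% with normal changes. With skewed volumes it covered 92 to 96% (24-hour zone diameters 1–3 or 2–4 cm, involution 30–70%, 15 or 17 tumours).

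**The case against.** Five points can be made for the plan.

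- **The split has a rationale.** If numbering is within patient, each stratum holds one tumour per patient and its observations are independent. This stands, so a reader should not infer that the planned tests are invalid. Averaging within patient keeps the same independence without the split.
- **The Wilcoxon floor binds on one branch only.** The SAP allows a paired t-test and names no normality test. Assuming Shapiro-Wilk at 0.05 and the skewed volumes of step 4 (log-SD of the volume ratio 0.30), normality is rejected in only about 5 to 15% of samples of three to five, so the t-test would usually be used. It then reaches p < 0.05 in roughly 8 to 34% of samples at n = 3 and 23 to 94% at n = 5. A reader might infer that small strata can never reach significance; the document does not support that. Low and uneven power does remain.
- **There is some ranking.** Item 3 puts the repeated-measures model first and the paired tests after it as additions. Within a tumour number the order is therefore clear. Only the choice between tumour numbers is open.
- **Larger precision gains could be quoted, but only against poor comparators.** Examples are the tumour 2 stratum, an interval rebuilt from the visit tables, or a pool that treats tumours as independent. The SAP does not plan the last two, and tumour 1 is the fair reference.
- **The SAP plans no confidence interval for any endpoint, asks for caution with every test, and already tabulates pooled volumes.** All true. But caution does not say which result answers the objective, and a table per visit does not pair a tumour with its own 24-hour volume.

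**Conclusion.** The point holds as a modest one. Item 3 answers the objective only through separate tests by an undefined tumour number, and the SAP contains no overall within-tumour change from 24 hours with an interval. That follows from the text and needs no assumption.

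The size does rest on assumptions. With 12 to 20 tumours in ten patients and an ICC of 0.2 to 0.8, the interval is about 1 to 18% narrower than for tumour 1 alone; in the example this is 0.4 to 1.7 points on 13.9. The real gain is a single interpretable estimate with a valid interval. If every patient has one tumour, tumour 1 is already the whole set, and the gain is only the stated change and its interval. It would be wrong to conclude that the trial's result is at risk: this is one secondary objective with no success criterion in the SAP. Severity: could be changed, as a cheap improvement.

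**What to change.** Reword section 15.2, item 3, as follows:

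- **Main result.** For each tumour, compute the change in ablation-zone volume from its own 24-hour value, both absolute and as a percentage of that value. Average within patient. Report the mean across patients with a t-based 95% confidence interval at 1 week, 1 month and 2 months.
- **Missing visits.** At each visit use only tumours with both the 24-hour volume and that visit's volume, and report the numbers of tumours and patients.
- **Re-treated tumours.** State which 24-hour scan is the reference.
- **Per-number results.** Keep them as a descriptive listing, and state how tumours are numbered across procedures.

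A mixed model may be added as a sensitivity analysis only.

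Cost: SAP wording and a little more analysis work, with no new data. Patients rather than tumours receive equal weight, which should be stated because the full analysis set is defined on tumours.
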